## Protocol summary

Protocol number	CACZ885D2310
Full Title	Phase 3 multicenter, randomized, double-blind, placebo-controlled study to assess the efficacy and safety of canakinumab on cytokine release syndrome in patients with COVID-19-induced pneumonia (CAN-COVID)
Brief title	Study of efficacy and safety of canakinumab treatment for CRS in participants with COVID-19-induced pneumonia
Sponsor and Clinical Phase	Novartis Phase III
Investigation type	Drug
Study type	Interventional
Purpose and rationale	
The purpose of this study is to evaluate the efficacy and safety of canakinumab for the treatment of cytokine release syndrome (CRS) in patients with COVID-19-induced pneumonia.
 
As of March 28, 2020, coronavirus disease 2019 (COVID-19) has been confirmed in 629,355 people worldwide. The mortality rate has been reported to be approximately 3.7%, compared with a mortality rate of less than 1% from influenza (Mehta et al 2020). There is an urgent need for effective treatment.
 
Accumulating evidence suggests that patients develop severe acute pneumonia due to COVID-19 with cytokine release syndrome (CRS). Currently, there is no clinical experience with canakinumab in the treatment of CRS, pneumonia or SARS-CoV-2 infection. However, the cytokine profiling of patients with severe COVID-19 that includes elevated levels of interleukin (IL)-2, IL-7, IL-6, IL-1, granulocyte-colony stimulating factor, interferon-<math>\gamma</math> inducible protein 10, monocyte chemoattractant protein 1, macrophage inflammatory protein 1-<math>\alpha</math>, tumor necrosis factor-<math>\alpha</math> and other pro-inflammatory cytokines suggests that canakinumab could improve patient outcomes (Mehta et al 2020; Zhou et al 2020).

Primary Objective	To demonstrate the benefit of canakinumab + SOC in increasing the chance of survival without ever requiring invasive mechanical ventilation among patients with COVID-19-induced pneumonia and CRS
Secondary Objectives	
 
• To demonstrate the benefit of canakinumab in reducing 4-week case fatality rate (CFR) among patients with COVID-19-induced pneumonia and CRS regardless of other subsequent clinical interventions
 
• To evaluate change from baseline in clinical serologic measurements related to CRS in COVID-19 patients with pneumonia
 
• To evaluate safety of canakinumab in patients with COVID-19-induced pneumonia and CRS
 

Study design	This is a Phase 3, multicenter, randomized, double-blind, placebo-controlled study to assess the efficacy and safety of canakinumab in patients with COVID-19-induced pneumonia and CRS. The study will enroll patients to canakinumab or placebo, in addition to standard of care per local practice, which may include anti-viral treatment, corticosteroids and/or supportive care. The total trial duration will be 126 days after the canakinumab or placebo dose. Safety will be closely monitored with an internal Novartis DMC during the study.

Study population	Approximately 450 patients with diagnosed COVID-19-induced pneumonia and CRS will be randomized to canakinumab or placebo in a 1:1 ratio
Key Inclusion criteria	
 
1. Male or female
 
2. Adults ≥ 18 years old (for US only: patients ≥ 12 years old)
 
3. Body weight ≥40 kg
 
4. Informed consent must be obtained prior to participation in this study. For US patients 12 - < 18 years old; parent/guardian consent must be obtained and assent if applicable.
 
5. Clinically diagnosed with SARS-CoV-2 virus by PCR or by other approved diagnostic methodology within 7 days prior to randomization
 
6. Hospitalized with COVID-19-induced pneumonia evidenced by chest x-ray or CT scan (taken within 5 days prior to randomization) with pulmonary infiltrates
 
7. SpO2 ≤ 93% on room air, or arterial oxygen partial pressure (PaO2)/fraction of inspired oxygen (FiO2) < 300mmHg (1mmHg=0.133kPa) (corrective formulation should be used for higher altitude regions (over 1000m))
 
8. C-reactive protein ≥20 mg/L or ferritin level ≥600 µg/L
 

Key Exclusion criteria	
 
1. History of hypersensitivity to canakinumab or to biologic drugs
 
2. Intubated and on mechanical ventilation (invasive) at time of randomization
 
3. Treatment with immunomodulators or immunosuppressant drugs, including but not limited to tocilizumab, TNF inhibitors and anti-IL-17 agents within 5 half-lives or 30 days (whichever is longer) prior to randomization with the exception of anakinra which is excluded within 5 half-lives only. Note: Immunomodulators (topical or inhaled) for asthma and atopic dermatitis and corticosteroids (any route of administration) are permitted
 
4. Suspected or known untreated active bacterial, fungal, viral, or parasitic infection with the exception of COVID-19
 
5. Neutropenia with ANC <1000/mm^3
 
6. Any serious medical condition or abnormality of clinical laboratory tests that, in the investigator's judgment, precludes the patient's safe participation in and completion of the study
 
7. In the opinion of the investigator, progression to death is imminent and highly likely within the next 24 hours, irrespective of the provision of treatments
 
8. Current participation in any other investigational trials
 

Study treatment	
Arm 1: Canakinumab 450 mg for body weight 40-<60 kg, 600 mg for 60-80 kg, or 750 mg for >80 kg in 250 mL of 5% dextrose infused IV over 2 hours
 
Arm 2: 250 mL of 5% dextrose infused IV over 2 hours
 
Canakinumab or placebo infusions will be prepared and blinded by an unblinded pharmacist or designated staff member.

Treatment of interest	Randomized canakinumab or placebo as described above. In addition, all patients will receive SOC per local practice for the treatment of COVID-19-induced pneumonia. The SOC may include anti-viral treatment, corticosteroids and/or supportive care.

Efficacy assessments	
The WHO 9-point ordinal scale of clinical status will be assessed on a daily basis at baseline and after study treatment during hospitalization as well as on Days 15, 29, 57 and 127
 
[REDACTED]

[REDACTED]	[REDACTED]
[REDACTED]	[REDACTED]
Key safety assessments	
Adverse event monitoring, physical examinations, and monitoring of laboratory safety values.

Other assessments	
[REDACTED]
 
Standard safety and laboratory assessment will be performed during hospital stay and outpatient visits after discharge from hospital (See Assessment Table).
 
In addition, CRS / [REDACTED]
 

• CRP

• Ferritin

 
[REDACTED]
 
[REDACTED]
 
[REDACTED]
 
Additional Laboratory measurements:
 

• Absolute neutrophil count

• Monocytes

• Lymphocytes

• Lactate dehydrogenase

• D-dimer levels

Data analysis	
An absolute increase of 15% survival without ever requiring invasive mechanical ventilation is considered a clinically meaningful benefit. A total sample size of 450 with 1:1 randomization ratio is planned for the study, which is expected to ensure at least 89% power for the primary analysis. Conditional on the rejection of null hypothesis in primary analysis, and if the true 4-week case fatality rate for the control arm is no less than 15%, there will be at least 70% power to prove if canakinumab leads to a 50% relative reduction in the risk of death.
 
The primary analysis will be performed after all patients complete Day 29 assessment or discontinue early from the study before Day 29. Final analysis will happen after all patients complete the study. The primary analysis follows a treatment policy strategy to estimate the difference and odds ratio between the response rates of canakinumab and control arms. Hypothesis testing will be performed based on the odds ratio estimated using a logistic regression model with study treatment, region and baseline

	
clinical status as covariates. The two-sided type I error will be controlled at 0.05.
 
Key secondary endpoint of 4-week case fatality rate (CFR) will be compared between the two treatment arms using a logistic regression model with study treatment, region and baseline clinical status as covariates. Using a hierarchical testing procedure for familywise 2-sided type I error control at 0.05, the hypothesis test in key secondary analysis will be performed if and only if the null hypothesis in the primary analysis is rejected.
 
Other secondary analyses will include descriptive summaries without hypothesis testing.
 
[REDACTED]
 
Safety summaries will be produced for regular DMC safety monitoring.

Key words	COVID-19 pneumonia, SARS-CoV-2, canakinumab

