Patients infected with SARS-CoV-2 present with a wide range of clinical severity varying from asymptomatic to a severe form of interstitial pneumonia, which may progress towards acute respiratory distress syndrome (ARDS) and/or multi organ failure and death. The clinical symptoms of COVID-19 patients include fever, cough, fatigue, loss of smell, and shortness of breath within 2-14 days after exposure ([CDC 2020](#)). SARS-CoV-2 uses the same receptor as SARS-CoV, angiotensin-converting enzyme 2 (ACE2) and mainly spreads through the respiratory tract ([Hoffmann et al 2020](#), [Xu H et al 2020](#), [Zhao D et al 2020](#)). Although currently, the pathogenesis of the pulmonary manifestations of COVID-19 remains poorly defined and knowledge of factors affecting disease severity is limited, underlying illnesses such as diabetes, cardiovascular diseases, hypertension, cancer and older age are associated with poorer outcome ([Huang et al 2020](#), [Chen et al 2020](#), [Guan et al 2020](#)). Cytokine profiling of patients with severe COVID-19 includes elevated levels of interleukin (IL)-2, IL-7, IL-6, IL-1, granulocyte-colony stimulating factor, interferon- $\gamma$  inducible protein 10, monocyte chemoattractant protein 1, macrophage inflammatory protein 1- $\alpha$  and tumor necrosis factor- $\alpha$  ([Wang et al 2020](#), [Mehta et al 2020](#), [Wan et al 2020](#), [Liu et al 2020](#), [Zhou et al 2020](#), [Diao et al 2020](#)).

COVID-19 associated pneumonia and ARDS have raised questions about the possible role of a cytokine storm in pathogenesis of SARS-CoV-2. Profound lung injury, in particular that of type II alveolar epithelial cells that express the viral entry receptor, ACE2, has the potential to activate intracellular pathogen sensing platforms called inflammasomes ([Chen et al 2019](#), [Xu H et al 2020](#), [Zhao and Zhao 2020](#)). Activated inflammasomes initiate cleavage of pro-IL-1 $\beta$  to active IL-1 $\beta$ , resulting in a robust pro-inflammatory response with activation and subsequent recruitment of neutrophils and macrophages with the normal physiological role of controlling

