### **8.2.1 Demographic/baseline characteristics information**

[figure not shown]
Demographic data to be collected at screening on all participants include: year of birth or age, gender, race, ethnicity and child-bearing potential (for females only).

Any relevant medical history including date of onset of COVID-19 disease symptoms, date of diagnosis of COVID-19 disease protocol solicited medical history, and/or current medical conditions before obtaining informed consent will be recorded in the Medical History CRF. Significant findings that are observed after the participant has provided informed consent and that meet the definition of an AE must also be recorded in the AE CRF. Whenever possible, diagnoses and not symptoms will be recorded.

Investigators will have the discretion to record abnormal test findings on the medical history CRF whenever in their judgment, the test abnormality occurred prior to the informed consent signature.

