## **12.5 Analysis of secondary endpoints/estimands**

### **12.5.1 Key secondary endpoint**

The key secondary endpoint is the COVID-19 related death during the 4-week period after study treatment. Hypothesis test for the key secondary analysis will be performed if and only if the null hypothesis for the primary analysis is rejected.

The null hypothesis for the key secondary analysis is that there is no difference in the COVID-19 related death rate (i.e. CFR) in patients treated with canakinumab compared to patients on placebo. The test of the hypothesis will be based on a logistic regression model adjusted for treatment, region and the baseline clinical status. The null hypothesis will be rejected if the observed p-value for treatment comparison (based on the CFR ratio) is less than the significance level of 0.05. Model-based estimates of the CFR and their 95% confidence intervals (CIs), estimate of the CFR ratio and 95% CI, and p-value for comparing canakinumab vs. placebo will be provided.

The number and percent of patients with COVID-19 related death during the 4-week period will also be provided by treatment arms.

The key secondary efficacy analysis is based on FAS. Patients who are lost to follow-up or discontinue early from study before Day 29 will be deemed as survivor if the latest clinical status is 0 or 1 on the 9-point ordinal scale. Otherwise, the patient will not be included in the analysis.

A sensitivity analysis will be provided by considering all patients who lost to follow-up or discontinue early from study before Day 29 as survivors.

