### **2.5.6 Supportive analysis**

The subgroup analyses (subgroups defined in [Section 2.2.1](#)) will be explored for the primary estimand and by fitting the data from each subgroup to the same logistic regression model as described for the primary analysis. In case of analyses on subgroups with extremely imbalanced sample sizes, the subgroup levels can be combined, if appropriate, while fitting the analysis model. The point estimate and 95% CI for odds ratio for each subgroup will be presented using forest plots.

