### 2.6.2 Statistical hypothesis, model, and method of analysis

The null hypothesis for the key secondary analysis is that there is no difference in the COVID-19 related death rate (i.e. CFR) in patients treated with canakinumab compared to patients on placebo. The alternative hypothesis is that there is a difference between the two treatment groups.

The superiority of canakinumab over placebo will be concluded if the odds ratio  $<1$  for the COVID-19 related death between canakinumab and placebo and the null hypothesis can be rejected at the two-sided significance level of 0.05.

The test of the hypothesis will be based on a logistic regression model with study treatment, region (North America vs. Europe), baseline clinical status based on the 9-point ordinal scale ( $\leq 4, \geq 5$ ) as factors. Model-based estimates of the CFR and their 95% confidence intervals (CIs), estimate of the odds ratio and 95% CI, and p-value for comparing canakinumab vs. placebo will be provided. In case of model converge problem caused by separability, Firth's penalized maximum likelihood estimation will be performed based on the same logistic regression model. The estimated odds ratio, p-values and 95% CI (all computed by penalized profile likelihood) will be presented.

The number and percent of patients with COVID-19 related death during the 4-week period will also be summarized by treatment arms. The difference in observed response rates between canakinumab and placebo arms will also be presented along with the asymptotic 95% confidence interval.

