### **2.6.4 Sensitivity analysis**

As a sensitivity analysis, the between group difference will also be assessed by rate difference using the marginal standardization method, for which the rate difference will be derived from the predicted rate for every patient as if they had received the study treatment or the placebo using a logistic regression model. The model will be adjusted by treatment, region (North America vs. Europe), and baseline clinical status based on the 9-point ordinal scale ( $\leq 4, \geq 5$ ) as factors. The rate within each treatment arm along with the 95% CI, rate difference along with the 95% CI and p-value will be presented.

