### 5.3.2 Key secondary analysis

The null hypothesis for the key secondary analysis is that there is no difference in the COVID-19 related death rate (i.e. CFR) in patients treated with canakinumab compared to placebo. The alternative hypothesis is that there is a difference between the two treatment groups.

The statistical superiority test based on odds ratio will be performed to compare the CFR between canakinumab and placebo arms and the same logistic regression model as described for the primary analysis will be used.

Same sensitivity analysis using the marginal standardization method as for the primary endpoint will also be provided for the key secondary endpoint.

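### In the readable text, neither confirmatory model adjusts for age, which the protocol links to worse outcome; adding it is a cheap, modest gain in power

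*Protocol*

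**What the plan says.** For the primary endpoint, the Data analysis row of the Protocol summary says: "Hypothesis testing will be performed based on the odds ratio estimated using a logistic regression model with study treatment, region and baseline" clinical status. For the key secondary endpoint, Protocol 12.5.1 says: "The test of the hypothesis will be based on a logistic regression model adjusted for treatment, region and the baseline clinical status". SAP 2.6.2 gives the same list in more detail: "logistic regression model with study treatment, region (North America vs. Europe), baseline clinical status based on the 9-point ordinal scale", dichotomised at 4 or below against 5 or above. The key secondary marginal-standardisation analysis in SAP 2.6.4 repeats it: "The model will be adjusted by treatment, region (North America vs. Europe), and baseline clinical status based on the 9-point ordinal scale". SAP 5.3.2 ties the two endpoints together: "the same logistic regression model as described for the primary analysis will be used".

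On age itself, Protocol 1.1 says that diabetes, cardiovascular disease, hypertension, "cancer and older age are associated with poorer outcome". Protocol 8.2.1 provides for its collection: "Demographic data to be collected at screening on all participants include: year of birth or age". Age is used for baseline summaries (SAP 2.3.2) and for subgroups (Protocol 12.4.7, SAP 2.2.1). Protocol 6.3.2 stratifies randomisation by country alone.

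Several places that could mention age cannot be read: Protocol 12.4.2, 12.4.5 and part of 12.4.7; SAP 2.5.2 (in part), 2.5.4, 5.3.1 and 5.3.1.1; and two blacked-out bullets in SAP section 4.

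**The concern.** In a logistic model, leaving out a baseline variable that predicts outcome pulls the treatment log odds ratio towards zero relative to its standard error. The planned test keeps its type I error but gives up some power. Here that applies to both tests that carry alpha. The second is reached only if the first rejects, and its stated power is only 70% at a 15% control fatality rate.

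Age is a natural candidate. The protocol names it as related to outcome, and it is a single continuous variable that does not depend on medical-history coding. Nothing in the randomisation controls its balance. A chance age difference between arms would go uncorrected in both tests, and results by age subgroup would not repair either one.

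**Working it through.** **1. The plan's own power figures.** Inputs are 225 per arm, two-sided alpha 0.05, and the rates in Protocol Tables 12-1 and 12-2. For an unadjusted Wald test on the log odds ratio:

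power = Φ(|ln OR| / SE − 1.96), with SE = √[1/(225·p_c(1−p_c)) + 1/(225·p_t(1−p_t))]

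- Response 50% vs 65%: ln 1.857 = 0.619; SE = √(1/56.25 + 1/51.19) = 0.193; 0.619/0.193 = 3.20; power 89.3% (stated 89%).
- Deaths 15% vs 7.5%: |ln 0.459| = 0.778; SE = √(1/28.69 + 1/15.61) = 0.315; 0.778/0.315 = 2.47; power 69.6% (stated 70%).
- The other rows give 88.8%, 90.5% and 94.2% for response and 91.6% and 83.1% for deaths. The stated values are 89, 90 and 94%, and 92 and 83%.

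The sample size is therefore not in error.

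**2. Power with and without age.** The documents give no age effect, so it was varied.

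- *Trials.* Each simulated trial had 450 patients in 8 countries, with permuted blocks of 4 within country and a two-sided Wald test at 0.05. There were 20,000 trials per power scenario. The planned model (treatment, US vs Europe, status ≥5) and the same model plus linear age were fitted to the same data, with marginal rates held at the plan's values.
- *Assumed inputs.* US 40%, Russia 20%, the other six countries 40% in total. Log odds ratios for a bad outcome: 0.2 for US, 0.4 for Russia and 1.0 for status ≥5 (30% of patients). Age standard normal, with correlation 0 or 0.3 with latent severity.

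Each cell shows the change in power points, then the gain in effective sample size, (mean z with age / mean z planned)² − 1. Ranges cover the two correlations.

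| Scenario (power of planned model) | age log-OR 0.3 per SD | 0.5 | 0.7 |
|---|---|---|---|
| Response 50 vs 65% (90.7–92.1%) | +0.3 to +0.7; 1.7–1.8% | +1.2 to +1.4; 4.6–4.9% | +2.1 to +2.3; 8.4–9.5% |
| Deaths 20 vs 10% (85.8–86.8%) | +0.3 to +0.5; 1.1–1.3% | +1.1 to +1.2; 3.1–3.3% | +1.7 to +2.0; 5.7–6.0% |
| Deaths 15 vs 7.5% (72.0–73.4%) | +0.4 to +0.6; 1.0% | +0.9 to +1.1; 2.7–2.8% | +2.2; 5.1–5.3% |

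The paired standard error is at most 0.18 points. In patients, the primary gain is 450 × 1.7–1.8% ≈ 8, 450 × 4.6–4.9% ≈ 21–22, and 450 × 8.4–9.5% ≈ 38–43.

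**3. If the age assumption is wrong.** The changes below are in table order.

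- Age has no effect: 0.0, −0.1 and +0.1 points.
- The true effect is a step (log-OR 1.0 above +0.33 SD) and linear age is fitted: +1.0, +0.5 and +0.7 points.

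**4. Type I error** (40,000 null trials per scenario, age log-OR 0.5). Overall it is 4.8–5.1% for both models. The two separate only when the arms differ in mean age by more than 1.96 × √(2/225) = 0.185 SD, which is about 1 trial in 20.

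- In those trials the primary test rejects a true null in 6.4–8.0% under the planned model and 4.2–4.5% with age. For deaths the figures are 6.9% and 5.5% (standard error 0.5–0.6 points).
- In the other 95% of trials both models are at 4.7–5.1%.

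**5. Different assumptions.** A second simulation used two regions of equal size, status odds ratio 2.5, region odds ratio 1.2 and age independent of status. The age odds ratios per SD were 1.25, 1.5, 2.0 and 2.5.

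- Response 50 vs 65%: 91.3→91.7%, 90.9→91.6%, 90.8→93.5%, 90.7→94.5%.
- Response 20 vs 35%: 95.5→95.9% at 1.5 and 94.9→96.6% at 2.0.
- Deaths 15 vs 7.5%: 72.5→73.0%, 73.5→73.9%, 71.3→73.4%, 72.1→75.7%.

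At an age odds ratio of 2.0 the estimated treatment odds ratio moves from 1.92 to 2.05 for response (50 vs 65%), and from 0.44 to 0.42 for deaths (15 vs 7.5%). This shows the attenuation directly.

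**6. Room for one more term.** At 15% vs 7.5%, 225 × 0.15 + 225 × 0.075 ≈ 51 deaths are expected, which can carry a model with four terms.

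**The case against.** The case for leaving the model alone is reasonable. The planned tests are valid and pre-specified, so an extra covariate is a choice and not a repair. The gain rests on an age effect that no document quantifies. It is under one point at the weak end, and the planned primary model already exceeds 89% power. Protocol 1.1 speaks of infected patients generally, concedes that knowledge is limited and names other conditions beside age. Being a subgroup factor proves little, since SAP 2.2.1 lists about twenty. The imbalance figures describe only the worst trial in twenty.

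Change also has a price. Protocol 14.1 requires a written, approved amendment. The SAP had already been amended in October 2020, shortly before the Day 29 lock. The DMC consists of sponsor staff with access to unblinded results, so a late change to the primary model must be visibly blind. The odds ratio, the SAP's stated summary measure, becomes conditional on age. Finally, the blacked-out text might already contain an age-adjusted analysis.

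Most of these points stand as limits on size and cost. They do not remove the case. The loss if age proves irrelevant is at most about 0.1 power point, and the trial team is blind until the lock. The marginally standardised rate difference keeps its meaning. SAP 5.3.2 also makes it unlikely that the unreadable primary model has a different covariate list.

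**Conclusion.** The concern holds as an improvement that should be made. It is not an error in the plan. Every readable covariate list for the two confirmatory tests omits age, although the protocol links age to outcome and collects it on all participants. For age log odds ratios of 0.3–0.7 per SD (odds ratios of about 1.35–2.0), adding age gains 0.3–2.3 power points on the primary test at 50% vs 65% and 0.3–2.2 points on deaths. That corresponds to 1.0–9.5% more effective sample size. Overall type I error is unaffected, and the main protection is against an unlucky age imbalance.

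The size depends on the assumed age effect and, to a lesser degree, on the assumed country mix, severity mix and covariate effects. The statement that age is absent is limited to the text that can be read.

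**What to change.** Before unblinding, add age as one continuous linear covariate to the primary and key secondary logistic models and to the marginal-standardisation sensitivity analyses. Keep region, baseline clinical status and the Firth fallback for deaths as planned. State how age is derived when only year of birth is recorded, and what is done if it is missing. Describe the odds ratio as conditional on the listed covariates.

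Record the change in SAP section 4, which now declares no changes to the primary and key secondary analyses. Amend the covariate lists in the protocol as Protocol 14.1 requires, and document that the blinded team made the decision.

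Also add a sentence allowing a reduced covariate set in small subgroups. SAP 2.5.6 plans on "fitting the data from each subgroup to the same logistic regression model as described for the primary analysis", but within a North America or a baseline-status subgroup the region or status term is constant and must already drop out.

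The cost is one parameter, a changed interpretation of the odds ratio, and the document edits with their approvals. No new data are needed.
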